8.2.3. Safety Analysis

8.2.3.1. Adverse Reactions

• All Adverse Reactions

Adverse reactions will be summarized by system organ class (SOC) and preferred term (PT) in terms of number and proportion of patients.

• Serious Adverse Reactions

Serious adverse reactions will be summarized by SOC and PT in terms of number and proportion of patients.

• Details of Adverse Reactions

Adverse reactions will be summarized by each of the categorizations below for each PT in terms of number and proportion of patients:

- Seriousness [serious, non-serious]
- Known/unknown [known, unknown]
- Action taken [permanent discontinuation, temporary discontinuation or dose reduction, others (none, dose increase)]
- Outcome [not recovered, recovered with sequelae, improved, resolved/recovered, unknown, death]

If the same patient experienced the same adverse reaction (of the same PT) more than once, the patient will be counted as follows:

- Seriousness: If the events include both serious and non-serious ones, the patient is counted as a
 patient experiencing a serious reaction.
- Known/unknown: If the events include both known and unknown ones, the patient is counted as
 a patient experiencing an unknown reaction.
- Time to onset (days): The first onset will be counted.
- Action taken: If multiple actions were taken, a single action will be chosen according to the
 order of priority of (1) permanent discontinuation, (2) temporary
 discontinuation/dose reduction, and (3) others (none, dose increase).
- Outcome: The outcome of the last event will be used.

• Major Investigation Items

The major investigation items listed below will be summarized in terms of number and proportion of patients:

- Hyperkalaemia
- Hypotension-related events

In addition, each major investigation item will be summarized by action taken and by outcome for each PT in terms of number and proportion of patients.

• Other Investigation Items

Renal impairment-related events will be summarized in terms of number and proportion of patients. In addition, the events will be summarized by action taken and by outcome for each PT in terms of number and proportion of patients.

• Onset Time of Adverse Reaction

All adverse reactions, hyperkalaemia, hypotension-related events, and renal impairment-related events will be summarized by time of first onset [Appendix A1.1] for each SOC and PT in terms of number of patients.

Relationship Between Concomitant Drugs and Adverse Reactions

To investigate the relationship between treatments for CHF/hypertension, or CYP3A4 inhibitors/other concomitant drugs requiring caution (any drug in the 3rd, 4th, 13th, 14th, 16th, or 17th drug groups, or a liskiren included in the 7th, listed) and adverse reactions of hyperkalaemia, hypotension-related events, or renal impairment-related events, patients experiencing hyperkalaemia, hypotension-related events, and renal impairment-related events will be summarized by PT in terms of number of patients, depending on whether they used CHF/hypertension treatments or whether they used CYP3A4 inhibitors/other concomitant drugs requiring caution (any drug in the 3rd, 4th, 13th, 14th, 16th, or 17th drug groups, or aliskiren included in the 7th, listed). Concomitant drugs used after the first onset of the relevant event will be excluded from the summarization.

• Adverse Reactions in Patients Excluded from the Safety Analysis Set

Adverse reactions occurring in CRF-collected patients who are excluded from the Safety Analysis Set will be presented in a tabular form. In addition, they will be summarized by SOC and PT in terms of number of patients.

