7.7. Data analyses

1) Definition of analysis sets

The safety analysis set (SAS) is defined as patients in whom treatment with this drug was confirmed.

The efficacy analysis set is defined as patients in whom treatment with this drug was confirmed and the efficacy could be evaluated in CHF patients.

2) Method of Analysis

(1) Safety analysis

Events for which a causal relationship with this drug cannot be ruled out will be handled as adverse reactions, and the number and proportion of cases of adverse reactions will be aggregated by System Organ Class and Preferred Term.

For patients with renal impairment, moderate renal impairment, or hepatic impairment, elderly patients (\geq 65 years, \geq 75 years), pediatric patients (<15 years), and diabetes patients with micro albuminuria or proteinuria, the safety will be comparatively investigated versus other populations.

In addition, the occurrence status of adverse reactions related to hyperkalaemia, renal impairment, or blood pressure decreased will be investigated in terms of risk factors and onset time.

(2) Efficacy analysis

Regarding each evaluation item for clinical evaluation, the number and proportion of cases will be aggregated by level from the results. Regarding the overall mortality and cardiovascular deaths in the study, the number of deaths and death rate (%), death rate (%) after 1 year observation period, death rate based on person-year method (the number of deaths in 100 person-year) will be calculated. For reference, the results will be compared to the domestic Phase III study or Japanese epidemiological surveys (CHART-1, CHART-2, JCARE-CARD, etc.). These comparisons will be performed with adjustment of factors such as patient background that are considered available or appropriate at the time of evaluation or setting of appropriate subgroups. ^{a)}

a. For the domestic Phase III study, comparisons to death rates adjusted for age, gender, and NYHA Functional Classification by using individual data such as patient background collected in the study will be considered; and for the Japanese epidemiological surveys, comparisons to death rates adjusted for gender and NYHA Functional Classification by using aggregate data such as patient background from published papers, etc. will be considered.

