8. STATISTICAL METHODS AND ANALYSES

Unless otherwise stated, for patients who completed treatment, data within the first 52 weeks (364 days) + 30 days (= 394 days) will be included in each statistical analysis. For patients who discontinued treatment, data until the first visit after discontinuation of treatment with Selara tablets, or the date 30 days after the last treatment, whichever comes first, will be included. For patients who died, all data will be included.

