11. APPENDICES

11.1. Appendix 1: Details of Data Extraction

A1.1 Definition of Visits for the Assessment of Dosing Status and Safety Endpoints

Visit	Endpoints	Representative date	Definition (time window)	
Baseline	Dosing status, safety endpoints	Day 1	From 30 days before the date of the first dose in this study (the date of the start of	
	outry trapellie		treatment) to the date of treatment start (before dosing)	
Week 1	Dosing status,	Day 7	From the date of treatment start (after	
	safety endpoints		dosing) to 17 days after treatment start	
Week 4	Dosing status, safety endpoints	Day 28	18-42 days after treatment start	
Week 8	Dosing status, safety endpoints	Day 56	43-70 days after treatment start	
Week 12	Dosing status, safety endpoints	Day 84	71-98 days after treatment start	
Week 16	Dosing status, safety endpoints	Day 112	99-126 days after treatment start	
Week 20	Dosing status, safety endpoints	Day 140	127-154 days after treatment start	
Week 36	Dosing status, safety endpoints	Day 252	155-266 days after treatment start	
Week 52	Dosing status, safety endpoints	Day 364	267-394 days after treatment start	
Final	Dosing status,		The time when the final visit for this study	
Visit	safety endpoints		is made	

If multiple sets of observation data are reported on different dates within a time window, data on the date closest to the representative one will be used for summarization/analysis. If two sets of data are reported on two dates equally close to the representative one, the data on the later date will be adopted. If there are multiple values observed on the same day, the mean value of them will be used.

A1.2 Definition of Visits for Cardiac Function Classification

Visit	Endpoints	Representative Date	Definition (time window)
Baseline	Left ventricular ejection fraction (LVEF), left ventricle internal dimensions in diastole (LVDd), left atrial dimension (LAD)	Day 1	From 180 days before the date of the first dose in this study (the date of the start of treatment) to the date of treatment start (before dosing)
Week 26	LVEF, LVDd, LAD	Day 182	From the date of the start of treatment (after dosing) to 182 days after treatment start
Week 52	LVEF, LVDd, LAD	Day 364	183-394 days after treatment start

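### Onset time is tabulated as patient counts over windows of 18 to 128 days, so a constant risk would show a false step up in the last two windows

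*SAP*

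**What the plan says.** Protocol 7.7 states that the occurrence of adverse reactions related to hyperkalaemia, renal impairment or blood pressure decrease "will be investigated in terms of risk factors and onset time". Protocol 7.3.10.1 and 7.3.10.2 set the same aim for hyperkalaemia and hypotension, the two major investigation items.

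The SAP meets that aim with one summary. Under Onset Time of Adverse Reaction in 8.2.3.1, the events "will be summarized by time of first onset [Appendix A1.1] for each SOC and PT in terms of number of patients". Most other adverse reaction tables in that section give a proportion as well as a number; this one does not.

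The windows come from Appendix A1.1, which also serves to choose the measurement nearest a visit date. The Week 1 row begins on the first treatment day, after dosing, and closes with "dosing) to 17 days after treatment start". Later rows include Week 4 ("18-42 days after treatment start"), Week 8 ("43-70 days after treatment start"), Week 36 ("155-266 days after treatment start") and Week 52 ("267-394 days after treatment start"). SAP section 8 sets the matching cut for patients who complete treatment: "data within the first 52 weeks (364 days) + 30 days (= 394 days) will be included in each statistical analysis".

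Kaplan-Meier estimation is specified for mortality only (SAP 8.1.4).

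**The concern.** A count of first onsets in a window depends on the hazard, the number of patients at risk and the length of the window. Here the length varies seven-fold across rows and nothing in the table corrects for it. A reader who runs down the column will see small numbers in the first five months and large ones afterwards, even if the risk never changes.

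Hyperkalaemia is an important identified risk in Protocol 6.1, and when it begins is a stated question of the study. The planned table could suggest that risk builds up late in treatment when it is constant, or even when it is highest early.

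**Working it through.** **Inputs.** Window limits: SAP Appendix A1.1. Planned size 1000 and assumed hyperkalaemia incidence 4.0% (59/1471) over 52 weeks (364 days): Protocol 7.5. Discontinuation: not given in the documents, so 0%, 30% and 50% by Week 52 are assumed, at a constant rate.

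**The plan's own figure.** 1000 × 0.040 = 40.0 expected cases, with exact binomial 2.5% and 97.5% points of 28 and 53. Both match Protocol 7.5.2.

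**Widths, counted inclusively.** Days 0–17 = 18; 18–42 = 25; four windows of 28; 155–266 = 112; 267–394 = 128. The total is 18 + 25 + 112 + 112 + 128 = 395 days. If adverse events end at Day 364, the last window is 267–364 = 98 days.

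**Width alone.** 128/18 = 7.1 and 98/18 = 5.4 for Week 52 against Week 1. Between adjacent rows, Week 36 against Week 20 is 112/28 = 4.0.

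**Expected counts under constant hazard.** h = −ln(1 − 0.040)/364 = 0.0001121 per day. With discontinuation proportion d by Day 364, c = −ln(1 − d)/364. A window from day a up to, but not including, day b holds 1000 × h/(h + c) × [exp(−(h + c)a) − exp(−(h + c)b)] first onsets.

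| Window | Width (days) | d = 0% | d = 30% | d = 50% |
|---|---|---|---|---|
| Week 1 | 18 | 2.0 | 2.0 | 2.0 |
| Week 4 | 25 | 2.8 | 2.7 | 2.6 |
| Week 8 | 28 | 3.1 | 3.0 | 2.8 |
| Week 12 | 28 | 3.1 | 2.9 | 2.6 |
| Week 16 | 28 | 3.1 | 2.8 | 2.5 |
| Week 20 | 28 | 3.1 | 2.7 | 2.4 |
| Week 36 | 112 | 12.3 | 10.0 | 8.2 |
| Week 52, to Day 394 | 128 | 13.8 | 10.0 | 7.4 |
| Week 52, to Day 364 | 98 | 10.6 | 7.8 | 5.8 |
| Week 52 / Week 1, to Day 394 | | 6.9 | 5.0 | 3.7 |
| Week 52 / Week 1, to Day 364 | | 5.3 | 3.9 | 2.9 |
| Week 36 / Week 20 | | 4.0 | 3.7 | 3.5 |

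The d = 0% ratios (6.9 and 5.3) lie slightly below the width ratios (7.1 and 5.4) because patients with a first event leave the risk set. The step remains at higher attrition: at 80% discontinuation the Week 52 / Week 1 ratio is still 1.7 (to Day 394), and it reaches 1 only at about 86% to 89%.

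**An early risk.** With the hazard tripled through Day 42 and no discontinuation, the counts are 4.9, 6.7, 2.5, 2.5, 2.5, 2.5, 9.9 and 11.2. The two largest still fall in the last two rows.

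**After correction.** Divided by person-time at risk, the constant-hazard data give 0.0001121 × 365.25 × 100 = 4.1 first events per 100 person-years in every window, whatever the discontinuation rate.

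**The case against.** Much can be said for the plan, and part of it stands.

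- **Part of the table is readable.** The Week 4 to Week 20 windows last 25 to 28 days and can be compared by count. In the tripled-risk example, the fall from 6.7 to 2.5 across near-equal windows does show the early excess. A reader might infer that the counts say nothing about early against late risk. That goes too far: the misleading parts are the step into the last two rows and, to a lesser degree, the short first row.
- **Attrition works the other way.** A reader might infer that the missing number at risk produces the false rise, or that patients leaving the study make it worse. The working shows the opposite: discontinuation lowers late counts and shrinks the step. The cause is window width, and a number-at-risk column alone would not cure it.
- **Seven-fold is an upper bound.** It needs full follow-up and events counted to Day 394. Protocol 7.2.6.1 and 7.3.8 end observation and adverse event entry at Week 52, while Protocol 9.2 and SAP section 8 allow about four weeks more. The last window is therefore 98 to 128 days.
- **Related tables exist.** SAP 8.2.1 tabulates discontinuations by the same visits, SAP 8.2.2 tabulates treatment duration by the same periods (also by eCLCr), and section 9 lists the individual events. They allow a rough estimate of the number on treatment, but the SAP does not link them to the onset table, and they neither give a rate nor correct for width.
- **A person-year formula exists.** SAP 8.1.4 applies it only where such a rate is presented, and its observation time is survival follow-up. That credits 364 days to a survivor who stopped the drug early and whose adverse event data ended soon after.
- **The analysis is descriptive.** SAP section 4 treats all tests as exploratory and sets no decision rule.

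**Conclusion.** The point holds as a matter of presentation and interpretation. Under constant risk, the planned onset table would show a step up in its last two windows because those windows are four or more times as long as the ones before them. Week 52 against Week 1 is about 7-fold (128-day last window) or 5.4-fold (98 days) with full follow-up, and about 3- to 5-fold with 30% to 50% discontinuation. These sizes rest on a constant hazard, the protocol's 4.0% incidence and assumed discontinuation rates.

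A reader might also infer that the safety conclusions as a whole are compromised. The documents do not support that: overall incidence and the subgroup risk ratios do not use these windows. What suffers is the answer to when events begin, which the protocol says it will investigate. The change is worth making before the results are interpreted.

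**What to change.** In SAP 8.2.3.1, for each onset window, add:

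1. the number of patients event-free and under adverse event observation at its start;
2. the observed person-time at risk within it;
3. first events per 100 person-years.

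Define person-time by the data cut that SAP section 8 applies to the events: for patients who discontinue, to the first visit after discontinuation or 30 days after last treatment, whichever is first; for completers, to Day 394. On-drug time would not match, because events after stopping are counted; survival follow-up would not match either. If adverse event entry in fact ends at Day 364, end both events and person-time there.

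Add a cumulative-incidence curve with numbers at risk for hyperkalaemia, overall and by eCLCr group.

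The cost is a few columns and one figure. Onset dates, dosing periods and the first consultation after discontinuation are already collected (Protocol 7.3.2, 7.3.3 and 7.3.8), so no new data are needed.

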5.4. Subgroup Analyses

The safety of study drug will be analyzed for each of the subgroups defined according to the following patient characteristics. The underlined one in each categorization will be used as the reference when a risk ratio is calculated:

- Hepatic impairment (as assessed by the physician) (present, absent, unknown)
- Renal impairment (as assessed by the physician) (present, absent, unknown)
- Estimated creatinine clearance (eCLCr)
 (<30 mL/min, 30 mL/min <50 mL/min, ≥50 mL/min, unknown)
- Not aged (<65 years old), Aged (≥65 years old)
- Children (<15 years old), Not children (≥15 years old)
- Young-old (\geq 65, <75 years old), Old-old + oldest-old (\geq 75 years old)
- Diabetes mellitus with microalbuminuria or proteinuria (present, absent, unknown)

Safety will also be analyzed for each of the subgroups defined according to the following factors:

- Use of a relevant treatment for CHF/hypertension (present, absent) (any of the 1st to 17th drug groups, except the 2nd and 15th which are contraindicated for coadministration, listed)
- Previous treatment with device therapy (present, absent, unknown)

NYHA class (I, II, III, IV, not assessed/unknown)

As a subgroup analysis, patients who may have violated any of the contraindications indicated in the package insert of Selara Tablets ("contraindication violators", hereinafter) will be extracted according to the criteria defined separately and the safety will be assessed for this subgroup.

The effectiveness of study drug will be analyzed for each of the subgroups defined according to the following patient characteristics:

- Hepatic impairment (as assessed by the physician) (present, absent, unknown)
- Renal impairment (as assessed by the physician) (present, absent, unknown)
- Estimated creatinine clearance (eCLCr)
 (<30 mL/min, 30 mL/min <50 mL/min, ≥50 mL/min, unknown)
- Not aged (<65 years old), Aged (≥65 years old)
- Children (<15 years old), Not children (≥15 years old)
- Young-old (\geq 65, <75 years old), Old-old + oldest-old (\geq 75 years old)
- Use of a relevant treatment for CHF/hypertension (present, absent)
- NYHA class (I, II, III, IV, not assessed/unknown)
- Treatment status (completed, discontinued)

If patients included in a subgroup for safety or effectiveness analysis are limited, reviewing individual patients will be considered instead of presenting a statistical summarization.

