8.2.3.4. Subgroup Analyses

For each of the categories defined in Section 5.4, the number and proportion of patients experiencing at least one adverse reaction will be presented. For each patient category, adverse reactions will also be summarized by SOC and PT in terms of number and proportion of patients.

According to Section 8.1.3, the risk ratio of one subgroup to the other will be presented for the incidence of adverse reactions (the proportion of patients experiencing adverse reactions) for each of the binary categorizations. The risk ratio will not be presented for a categorization if <10 patients are included in one category in the categorization and the analysis of risk ratio is determined to be difficult after the categorization is reviewed.

Similar subgroup analyses will be performed also for serious adverse reactions and SAEs.

Adverse reactions occurring in contraindication violators will be tabulated and, as necessary, will be summarized by SOC and PT in terms of number and proportion of patients.

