If multiple sets of observation data are reported on different dates within a time window, data on the date closest to the representative one will be used for summarization/analysis. If two sets of data are reported on two dates equally close to the representative one, the data on the later date will be adopted. If there are multiple values observed on the same day, the mean value of them will be used.

A1.3 Definition of Visits for the Assessment of Plasma BNP and Serum NT-proBNP

Visit	Endpoints	Representative date	Definition (time window)
Baseline	Plasma BNP, serum NT-proBNP	Day 1	From 90 days before the date of the first dose in this study (the date of the start of treatment) to the date of treatment start (before dosing)
Week 13	Plasma BNP, serum NT-proBNP	Week 91	From the date of treatment start (after dosing) to 91 days after treatment start
Week 26	Plasma BNP, serum NT-proBNP	Day 182	92-182 days after treatment start
Week 39	Plasma BNP, serum NT-proBNP	Day 273	183-273 days after treatment start
Week 52	Plasma BNP, serum NT-proBNP	Day 364	274-394 days after treatment start

If multiple sets of observation data are reported on different dates within a time window, data on the date closest to the representative one will be used for summarization/analysis. If two sets of data are reported on two dates equally close to the representative one, the data on the later date will be adopted. If there are multiple values observed on the same day, the mean value of them will be used.

11.2. Appendix 2: An Example of Table Showing Risk Ratios Regarding the Incidence of Adverse Reaction

Event name: Increased XXX	Category 1		Categor	Category 2		Risk ratio (RR)	
1	n/N	(%)	n/N	(%)	RR	95% CI	
Sex (male vs. female)	18 / 2220	(0.8)	3 / 1099	(0.3)	2.97	(0.88 - 10.06)	
Aged (≥65 yrs) vs. Not aged (<65 yrs)	19 / 2788	(0.7)	2 / 531	(0.4)	1.81	(0.42 - 7.74)	
Diagnosis (disease A vs. disease B)	3 / 221	(1.4)	18 / 3098	(0.6)	2.34	(0.69 - 7.87)	
Duration of disease (<1 year vs. ≥1 year)	9 / 771	(1.2)	7 / 866	(0.8)	1.44	(0.54 - 3.86)	
Concomitant use of drug A (present vs. absent)	9 / 798	(1.1)	12 / 2521	(0.5)	2.37	(1.00 - 5.60)	
Pretreatment with drug A (present vs. absent)	1 / 148	(0.7)	20 / 3171	(0.6)	1.07	(0.14 - 7.93)	
Coexistence of disease B (present vs. absent)	16 / 1614	(1.0)	5 / 1703	(0.3)	3.38	(1.24 - 9.20)	
Past history of disease B (present vs. absent)	7 / 674	(1.0)	14 / 2643	(0.5)	1.96	(0.79 - 4.84)	

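### The concomitant-drug table counts only patients with the event and pools CYP3A4 inhibitors with other caution drugs, so no output described in the SAP compares reaction risk in CYP3A4-inhibitor users and non-users

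*SAP*

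**What the plan says.** - **The table.** In SAP 8.2.3.1, the item on concomitant drugs and adverse reactions takes patients who had one of the three grouped reactions and counts them by PT, "in terms of number of patients, depending on whether they used CHF/hypertension treatments or whether they used CYP3A4 inhibitors/other concomitant drugs requiring caution". The caution class is any drug in groups 3, 4, 13, 14, 16 or 17, or aliskiren from group 7.
- **Timing of use.** "Concomitant drugs used after the first onset of the relevant event will be excluded from the summarization".
- **The only drug-use factor with a risk ratio.** Under SAP 5.4 and 8.2.3.4 this is use of any relevant CHF/hypertension treatment, defined as "any of the 1st to 17th drug groups, except the 2nd and 15th which are contraindicated for coadministration, listed".
- **Contraindication violators.** This group "will be extracted according to the criteria defined separately and the safety will be assessed for this subgroup" (5.4). In 8.2.3.4: "Adverse reactions occurring in contraindication violators will be tabulated and, as necessary, will be summarized by SOC and PT".
- **Listing.** SAP section 9 lists CYP3A4-inhibitor users who had adverse reactions.
- **Protocol.** Section 6.1 names CYP3A4-inhibitor use as an Important Potential Risk. Section 7.3.4.1.1 marks ACE inhibitors and ARBs as caution drugs as well. Section 7.3.4.1 collects drug names and treatment periods for all subjects. Section 7.7 says the occurrence of these reactions will be examined for risk factors, without naming a drug or a measure.

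**The concern.** A relationship between a drug and a reaction needs the risk with the drug and the risk without it. The table gives neither, because patients without the event do not appear. A count of user cases against non-user cases depends mostly on how common the drug is and can point the wrong way.

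Pooling is a second problem. ACE inhibitors and ARBs are caution drugs and are also named in the indication as standard treatment. A class that includes them could cover most patients, and a signal confined to CYP3A4 inhibitors would then be diluted even if denominators were added.

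At stake is the one quantitative summary aimed at a risk that the protocol itself lists. If the plan is followed exactly, it cannot answer the question that the section poses.

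**Working it through.** **1. The SAP's own example (Appendix 2, concomitant use of drug A).** Inputs: 9/798 users and 12/2521 non-users.
- RR = (9/798)/(12/2521) = 1.128%/0.476% = 2.37.
- SE of log RR = sqrt(1/9 - 1/798 + 1/12 - 1/2521) = 0.439. The 95% CI is 2.37 × exp(±1.96 × 0.439) = 1.00-5.60. Both figures match the SAP.
- The 8.2.3.1 format would keep only 9 v 12, which looks like fewer cases on the drug. In fact users are 798/3319 = 24% of patients and 9/21 = 43% of cases.

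**2. The same counts fit opposite conclusions.** Protocol 7.5.2 expects 1000 × 4.0% = 40.0 hyperkalaemia reactions. Suppose, for illustration, that 4 are in CYP3A4-inhibitor users. The table shows 4 v 36 whatever the number of users:

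| Users among 1000 (assumed) | RR (95% CI) |
|---|---|
| 20 | 5.44 (2.14-13.85) |
| 50 | 2.11 (0.78-5.70) |
| 100 | 1.00 (0.36-2.75) |
| 200 | 0.44 (0.16-1.23) |

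**3. Dilution by pooling.** Assume that the pooled class covers 90% of patients, that a share c of all patients use CYP3A4 inhibitors, and that only those users have RR 2. The pooled class then shows RR = ((0.90 - c) + 2c)/0.90. This is 1.02, 1.06 and 1.11 for c = 2%, 5% and 10%.

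**4. Do other described outputs fill the gap?**
- *Risk-ratio factor in 5.4/8.2.3.4:* groups 1-17 without 2 and 15 contain every numbered caution group (3, 4, 7, 13, 14, 16, 17). The factor is broader than the pooled class and cannot isolate any of them.
- *Contraindication violators:* one group over all contraindications, with no comparison specified.
- *Section 9 listing:* numerators only.
- *Medication categories in 8.2.2:* these may give user counts, but the categories are not shown. The rule on drugs used after onset can apply only to patients who had an event, so such counts may not match the table.

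**5. Precision of a separate CYP3A4 row.** N = 1000. Total events are 40 (hyperkalaemia) and 12 (renal impairment), from Protocol 7.5.2. The documents give no use rate, so 2%, 5% and 10% are assumed. Expected user cases = E × RR × n1/(RR × n1 + n0), where E is total events and n1 and n0 are users and non-users. The CI formula is that of step 1.

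| Reaction, true RR | Use | Expected cases, users v non-users | Expected 95% CI |
|---|---|---|---|
| Hyperkalaemia, 2 | 2% | 1.57/20 v 38.43/980 | 0.43-9.27 |
| Hyperkalaemia, 2 | 5% | 3.81/50 v 36.19/950 | 0.72-5.53 |
| Hyperkalaemia, 2 | 10% | 7.27/100 v 32.73/900 | 0.92-4.35 |
| Hyperkalaemia, 1 | 5% | 2.00/50 v 38.00/950 | 0.25-4.03 |
| Renal impairment, 2 | 5% | 1.14/50 v 10.86/950 | 0.30-13.46 |

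For renal impairment with RR 2, the chance of no user case at all is 62%, 32% and 11% at 2%, 5% and 10% use. The protocol gives no expected count for hypotension. The fewer-than-10-patients rule in 8.2.3.4 would come into play only below 10/1000 = 1% use.

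**The case against.** **No commitment is missed.** Protocol 7.7 names the populations to be compared, and CYP3A4-inhibitor users are not among them. The SAP treats all tests as exploratory and gives these users a dedicated listing. This stands. A reader might infer that the SAP departs from the protocol, but a general reference to risk factors does not support that.

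**The new row would be weak.** This also stands. At 5% use, the intervals for RR 2 and RR 1 overlap almost wholly, and renal impairment may have no user case. The gain is a denominator and an honest interval, not a decisive comparison. A bare count hides the same uncertainty.

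**The 9 v 12 contrast comes from a template row.** True. It shows how the format misleads; it does not size the effect in this study.

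**A start-date exposure rule could be worse.** A patient who begins an inhibitor later and then has the reaction would count as unexposed, whereas the current table counts use before onset. This is right and shapes the fix.

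**The negative cannot be fully verified.** A reader might conclude that no comparison will exist anywhere. The documents do not support that: the medication categories, the numbered drug list and the authority's Attachment Forms (SAP section 9) are not shown. Only the outputs described can be judged.

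**The 15th drug group.** Both drug-class definitions omit it, and 5.4 calls it contraindicated. A reader might infer that potent CYP3A4 inhibitors are being counted as unexposed. The numbering does not match the order in Protocol 7.3.4.1.1 at items 13-15, so the group's content is unknown and this is only a query.

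**Conclusion.** The concern holds for the outputs that the SAP describes. The 8.2.3.1 table has no denominators and does not separate CYP3A4 inhibitors, so it cannot show whether their use goes with a higher risk of the three reactions. Nothing else described makes that comparison.

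The defect in the format rests on the SAP's own example and needs no assumption. The dilution and precision figures rest on assumed use rates (2-10%), an assumed 90% coverage of the pooled class and the protocol's expected counts. They are illustrative.

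This is a worthwhile, cheap improvement rather than a breach. Individual CYP3A4 cases remain visible in the listing. The added rows would be post hoc, since SAP version 7.0 (19 November 2020) records observation as completed.

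**What to change.** - **Add one table.** For each of the three grouped reactions, give n/N (%) and RR (95% CI) for users versus non-users in the Appendix 2 format. Put CYP3A4 inhibitors in their own row, separate from ACE inhibitors/ARBs and from the other caution drugs.
- **Use one exposure rule for patients with and without the event.** Preferably report events per person-time on and off the drug up to first onset, from the treatment periods already collected, so that later courses count. The observation time in 8.1.4 follows survival status, so person-time here needs its own definition based on the safety data window in section 8.
- **Optional simpler supplement.** Compare by use on the Selara start date, excluding drugs that 8.2.2 classes as pretreatment, and state that this misses later courses.
- **Small groups.** Apply the 8.2.3.4 rule and the 5.4 provision that "reviewing individual patients will be considered instead of presenting a statistical summarization". Give n/N and refer to the listing.
- **Keep** the case table and the listing. Label the new rows post hoc, unadjusted and descriptive.
- **Query.** Confirm what the 15th drug group contains. If it holds CYP3A4 inhibitors, count its users as exposed.

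The cost is SAP wording and programming for one table with a few drug rows; the on/off-drug rates take somewhat more work. No new data are needed, and the RR format already exists (8.1.3, Appendix 2). The downside is an imprecise, unadjusted CYP3A4 row that must not be read as a test.
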